8.1.2 Hypotheses/Sample Size

Ten (10) articles²⁻¹¹ were identified to be reporting on “pain reduction,” representing 392 evaluable patients. One of these articles¹⁰ did not report on “related SAE rate”; thus, for this endpoint we used 9 articles^{2-9,11}, representing 386 evaluable patients. The table below provides by-publication “pain reduction” and “related SAE” rate used to conduct respective meta-analyses.

Meta-analyses were conducted using a random effects model. The sample sizes were calculated using SAS version 9.4.

Table 8.1.2-1: Pain Reduction and Related SAE Rates by Publication

Study	“Pain Reduction”	“Related SAEs”
Eleftheriadis 2005 ²	62% (62/100)	25% (25/100)
Vitale 2004 ³	83% (62/75)	19% (17/89)
Topazian 2005 ⁴	60% (9/15)	47% (7/15)
Costamagna 2006 ⁵	84% (16/19)	0% (0/19)
Farnbacher 2006 ⁶	55% (53/96)	28% (27/96)
Ishiara 2006 ⁷	78% (7/9)	0% (0/9)
Cahen 2007 ⁸	32% (6/19)	26% (5/19)
Weber 2007 ⁹	82% (14/17)	12% (2/17)
Seza 2011 ¹⁰	85% (17/20)	N/A
Gabrielli 2005 ¹¹	32% (7/22)	32% (7/22)

August 28, 2017

Boston Scientific
WallFlex Pancreatic Pivotal Protocol
91067616 Rev/Ver AK
Page 33 of 64

Pain reduction

For “pain reduction” the meta-analysis yielded a point estimate of 66% with a 95% Confidence Interval (CI) from 53% to 76%.

Statistical testing will be performed to determine if the probability of “pain reduction” when using the WallFlex Pancreatic Stent is greater than the performance goal (PG) set at 53%, the lower bound of the 95% CI from the meta-analysis above. Hence, the following hypothesis will be tested:

$$H_0: \pi_1 \leq 53\%$$

$$H_a: \pi_1 > 53\%$$

where π_1 is the probability of observing “pain reduction”.

Assuming that the observed probability is 75%, 43 patients will be required for the above hypothesis, with a one-sided alpha of 0.025 and power of 80%.

The observed probability of pain reduction was set to 75% given that 8 out of 10 patients in a 10 patient pilot study remained stent free at 6 months post-removal. The primary effectiveness endpoint will be assessed in two ways, namely one using last observation carried forward for patients that are missing 6 month pain data and one counting patients with 6 month pain data as failures. A tipping point analysis will be performed to assess the validity of the associated conclusions.

Related SAEs

For “related SAE rate” the meta-analysis yielded a point estimate of 25% with a 95% CI from 19% to 32%.

Statistical testing will be performed to determine if the probability of “related SAE rate” is lower than 32%, the upper bound of the 95% CI of the meta-analysis. Hence, the following hypothesis will be tested:

$$H_0: \pi_2 \geq 32\%$$

$$H_a: \pi_2 < 32\%$$

where π_2 is the probability of observing “related SAE rate”.

Assuming that the observed probability is 15%, 57 patients will be required for the above hypothesis, with a one-sided alpha of 0.025 and power of 80%.

The observed probability of the related SAE rate was set to 15% given what was observed in a 10 patient pilot study and the resulting mitigation measures put in place to reduce the risk of observed related SAEs per definition of the Primary Safety Endpoint.

The primary safety endpoint will be assessed in two ways, namely one using all related SAEs (excluding pain thought to be caused by stent expansion per Section 4.2) and one using all related SAEs except those termed as pain by the site.

Sample size

August 28, 2017

[figure not shown]
Boston Scientific
WallFlex Pancreatic Pivotal Protocol
91067616 Rev/Ver AK
Page 34 of 64

Taking the largest of the two sample sizes, namely 43 and 57, and compensating for possible loss of patients after enrollment, an additional 10% of patients will be required, for a total of 64 Intent-to-Treat patients.

The percentage of patients who do not meet the inclusion criteria levels of the VAS pain score (≥ 20) and frequency of pain score (50, 75, or 100) at the time of study stent placement, due to a prior single plastic pancreatic stent, is anticipated to range from 20-30%. Therefore, we propose to enroll up to 92 patients so as to have 64 patients who met the inclusion criteria levels of the VAS pain score (≥ 20) and frequency of pain score (50, 75, or 100) at the time of study stent placement. No more than 28 subjects who do not meet these inclusion criteria at the time of study stent placement will be enrolled into the study.

Forest plots illustrating the two meta-analyses and marking the selected PG and assumed observed probability are provided below.

[figure not shown]
Meta-Analysis of Pain

Meta-Analysis of SAE

August 28, 2017

Boston Scientific
WallFlex Pancreatic Pivotal Protocol
91067616 Rev/Ver AK
Page 35 of 64

NOTE: A literature search was performed on metal pancreatic stenting, and 4 articles that represented 61 patients¹³⁻¹⁶ were found. The meta-analyses yielded a point estimate of 84% with a 95% CI of (72%, 92%) and 19% with a 95% CI of (8%, 38%) for “pain reduction” and “related serious adverse events,” respectively. These are similar to the findings of the meta-analyses for plastic pancreatic stenting.

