6.1.2 Intent-to-Treat Cohort

This cohort (ITT) consists of those “enrolled” patients who meet all inclusion/exclusion criteria. Any adverse events occurring or resulting from a treatment attempt will be collected. Protocol deviations will be collected as necessary. Patients in this cohort will be counted towards the enrollment ceiling, and this cohort will be considered the primary analysis cohort.

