8.1.3 Sensitivity Analyses

Sensitivity analyses, specifically a tipping-point analysis for the primary endpoint, may be conducted to assess the impact of missing data on interpretation of the results. Missing equals failure method will be used, such that missing data will be added into the primary analyses as failures until the null hypotheses are not rejected any longer. Multiple imputation methods will not be used.

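### The primary effectiveness endpoint is analysed two ways for missing 6-month pain data; neither is named as deciding the test against 53%, one is misprinted, and LOCF may use in-stent scores

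*Combined protocol and SAP*

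**What the plan says.** Section 8.1.2 tests whether the pain-reduction rate exceeds 53%, at one-sided alpha 0.025; the synopsis adds that the test is exact. On missing data, 8.1.2 says: "The primary effectiveness endpoint will be assessed in two ways, namely one using last observation carried forward" for patients "missing 6 month pain data and one counting patients with 6 month pain data as failures". It continues: "A tipping point analysis will be performed to assess the validity of the associated conclusions".

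Section 8.1.3 describes sensitivity analyses, "specifically a tipping-point analysis for the primary endpoint, may be conducted". There, missing patients are added to the primary analyses as failures until the null hypothesis is no longer rejected. Section 6.1.2 says of the ITT cohort that "this cohort will be considered the primary analysis cohort".

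Under 8.1.1 the endpoint falls 6 months after stent removal or observed migration. Success also depends on the average daily narcotic dose at that time. Migration with recurring pain, and restenting for recurring pain, are failures by definition. Pain is scored at every visit (7.1): baseline, stent placement, months 1 and 3 with the stent in place, just before removal, 3 and 6 months after removal, and at unscheduled visits. Sections 6.3 and 6.4 foresee patients who withdraw or stop responding with the stent in place.

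**The concern.** The two versions treat the same patients differently, so they can give different answers to the one primary effectiveness question. The ITT statement settles who is analysed, not how a missing score counts. A tipping-point analysis tests how robust a result is; it does not say which result is the trial's. If the versions disagree, the plan has no explicit rule, and the choice would be made with the data in view. In a single-arm study, outcomes become visible as they accrue.

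Two further faults sit in the same sentence.

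- **Misprint.** The failure version names patients *with* 6-month data as failures.
- **LOCF source.** Nothing limits which visit is carried. The endpoint asks whether relief lasts after the stent is out, whereas a score at month 1 or 3, or just before removal, reflects a stent still in place. LOCF is also defined for pain data only and gives no rule for a missing 6-month narcotic dose.

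**Working it through.** **Inputs.** From 8.1.2 and the synopsis: null rate 53%, planning rate 75%, one-sided alpha 0.025, exact test, and "an additional 10% of patients will be required, for a total of 64 Intent-to-Treat patients". Other true rates considered: 66% (plastic-stent meta-analysis, 8.1.2) and 84% (metal-stent note, 8.1.2). Assumed, because the documents give no figure: the number missing, the number k who have a score to carry, and the success rate q among carried scores (53% to 95%).

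**The plan's own figure.** For n = 43 the smallest c with P(X ≥ c | 43, 0.53) ≤ 0.025 is 30 (alpha 0.0190), and power at 75% is 83.4%. From n = 43 upward power stays at or above 80%. The stated 43 reproduces.

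**Decision rule at n = 64.** The smallest c is 43 (alpha 0.0150); 42 gives 0.0280. Power at 75% with nothing missing is 94.0%.

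**Direction of disagreement.** Reading *without* for *with*, LOCF never counts fewer successes than missing-as-failure. So requiring either to pass is the same as LOCF, and requiring both is the same as missing-as-failure. Only missing patients whose carried score is a success matter. A carried baseline is a failure: eligible scores have VAS of at least 20 and frequency of at least 50, so the mean is at least (20 + 50)/2 = 35, which is above 10 and shows no reduction.

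**Example.** Six missing, 41 successes among 58 observed. Missing-as-failure: 41/64, one-sided p = 0.049, fails. LOCF with 4 of 6 carried as successes: 45/64, p = 0.0036, passes. With all 6 carriable, any count from 37 to 42 of 58 can split the verdicts, since 37 + 6 = 43.

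**Chance of opposite verdicts** = P(Bin(64 − m, p) + Bin(k, q) ≥ 43) − P(Bin(64 − m, p) ≥ 43), with m missing and true rate p. Ranges are for q from 53% to 95%.

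| True rate | 3 missing, 3 carriable | 6 missing, 3 carriable | 6 missing, 6 carriable |
|---|---|---|---|
| 66% | 16% to 30% | 12% to 24% | 28% to 54% |
| 75% | 8% to 13% | 15% to 25% | 25% to 35% |
| 84% | 0.2% | 1% to 2% | about 2% |

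For 75% with all 6 carriable: missing-as-failure passes with probability 0.628; LOCF with 0.881 (q = 53%), 0.940 (q = 75%) and 0.974 (q = 95%). With 1 missing at 75% the difference is 2% to 3%, and with 2 it is 5% to 8%.

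**LOCF source (illustrative).** If the true 6-month rate is 53% but k carried scores succeed at rate q, type I error is P(Bin(64 − k, 0.53) + Bin(k, q) ≥ 43):

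| k | q = 65% | q = 80% | q = 95% |
|---|---|---|---|
| 1 | 1.6% | 1.8% | 1.9% |
| 2 | 1.7% | 2.1% | 2.4% |
| 3 | 1.9% | 2.4% | 3.0% |
| 4 | 2.0% | 2.8% | 3.7% |
| 7 | 2.47% | 4.3% | 6.9% |

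The 65% and 95% are the ends of the range quoted in section 1.1 for relief straight after pancreatic stenting in general. They are not estimates for this endpoint.

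**Power if missing-as-failure decides**, with 75% success among completers and missing fraction f: P(Bin(64, 0.75(1 − f)) ≥ 43) = 94% (f = 0), 81% (f = 5%), 58% (f = 10%).

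**The case against.** The best defence is that the hierarchy can largely be recovered. Section 8.1.3 files missing-equals-failure under sensitivity analyses and adds failures step by step, which makes sense only if missing patients are not already failures in the primary analysis. Both versions and a tipping-point analysis are announced in advance, so a reader would see any disagreement. This stands in part: it points away from missing-as-failure. It does not select LOCF, because adding missing patients fits a completers analysis at least as well, and 8.1.2 presents both versions as assessments of the primary endpoint.

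The size also rests on assumptions. The 10% in 8.1.2 allows for loss after enrolment generally and is not a forecast of missing 6-month scores. Some patients with poor outcomes are already failures by definition. With 1 or 2 missing the risk at 75% is small. All of this stands, and it is why ranges are given.

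Three stronger readings are tempting and not supported. A reader might infer that the plan really fails everyone who has 6-month data; the missing-equals-failure wording in 8.1.3 shows that this is a slip. A reader might infer two chances at success; the versions are nested, so at most the more lenient one decides. A reader might infer that LOCF inflates type I error in this trial; 6.3 and 6.4 provide for patients leaving with the stent in place but give no number, and 6.4 requires extra attempts to bring unresponsive patients back.

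**Conclusion.** The concern holds. No section names the version that decides the primary effectiveness test, the failure rule is misprinted, and LOCF may draw on in-stent scores. The sample size of 43 is not at fault.

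The effect runs from negligible to large. With 6 of 64 missing (9%) and all carriable, opposite verdicts have a chance of 25% to 35% at a true rate of 75% and 28% to 54% at 66%. At 84%, or with only 1 missing at 75%, the chance is about 3% or less. These figures assume 64 patients in the effectiveness analysis, the stated numbers missing, carried success of 53% to 95%, and no loss through a missing narcotic dose.

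The LOCF source fault is one of definition, and its numerical effect is illustrative. Type I error stays under 2.5% with 1 or 2 carried scores at the rates tried, and exceeds it from 3 carried at 95% success or 4 at 80%.

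**What to change.** Amend 8.1.2 and 8.1.3:

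1. Name one version as deciding the test against 53% and the other as sensitivity.
2. In the failure version, change *with* to *without* 6-month pain data.
3. Let LOCF use only scores recorded after the study stent is out, that is, after removal or observed complete distal migration, and count a patient with no such score as a failure. Partial migration is left out because the stent may still be in place. Apply the same rule to a missing 6-month narcotic dose; otherwise a patient missing both has no defined outcome under LOCF.
4. Make the tipping-point analysis either planned or optional in both sections, and define the analysis it starts from. The present wording about adding missing patients needs changing under either version: missing-as-failure leaves none to add, and LOCF has already counted those with a score.
5. If missing-as-failure is chosen, state its power with the missingness assumed, as in the last line of the working.

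The cost is wording only, with no added patients or visits. The drawback is that the stated power may look less favourable. The change should be made before 6-month outcomes are examined.

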	
Pain will be scored between 0 and 100 as the mean of the VAS Pain Score and Frequency of Pain sectors of the Izbicki pain scale.
 
Complete pain relief is defined as pain score ≤ 10, and partial pain relief is defined as pain score > 10 and reduced by at least 50% compared to baseline.
 
Complete or partial pain relief in the setting of a 50% higher average daily narcotic dose will be considered a primary effectiveness endpoint failure. Average daily narcotic dosage for prior month will be assessed at baseline visit prior to plastic or study stent placement, whichever is implanted first, and at 6 months post-stent removal/observation of complete distal migration.
 
Patients who experience stent migration in setting of recurring pain (VAS Pain Score of ≥ 20) will be considered as having failed the primary effectiveness endpoint.
 
Patients who are restented in the setting of recurring pain will be considered as having failed both the primary effectiveness endpoint and the secondary endpoint for stricture resolution and may only be restented with a non-study stent.
 
Restenting with a new study stent may only occur during the initial stent placement procedure for such situations as stent misplacement, improper stent size choice, or other conditions, as necessary and will not be considered a primary effectiveness endpoint failure or a secondary endpoint failure for stricture resolution.
 
Primary Safety Endpoint:
 
Rate of related Serious Adverse Events (SAEs) from WallFlex Pancreatic stent placement to end of study.
 
Relatedness will be determined by the PI, reporting if the SAE is related to the study stenting procedure, to the indwelling study stent, to study stent removal and/or to study stent migration.
 
Pain thought to be caused by WallFlex Pancreatic stent expansion will be reported, but will not count towards the endpoint if all three of the following conditions apply:⁵
 
 1. Pain can be managed by medication, with the exception of injectable narcotic use for more than 24 hours. 2. Pain does not cause WallFlex Pancreatic stent removal. 3. Pain resolves by 72 hours after WallFlex Pancreatic stent placement.
Secondary Endpoints	
Effectiveness
 
 1. Stricture Resolution

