4.2 Primary Safety Endpoint

Primary Safety Endpoint:

Rate of related SAEs from WallFlex Pancreatic stent placement to end of study.

Relatedness will be determined by the PI, reporting if the SAE is related to the study stenting procedure, to the indwelling study stent, to study stent removal and/or to study stent migration.

Pain thought to be caused by WallFlex Pancreatic stent expansion will be reported, but will not count towards the endpoint if all three of the following conditions apply:

1. Pain can be managed by medication, with the exception of injectable narcotic use for more than 24 hours.
2. Pain does not cause WallFlex Pancreatic stent removal.
3. Pain resolves by 72 hours after WallFlex Pancreatic stent placement.

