For the patients who have a single plastic stent in place for up to 90 days before receiving the study stent, inclusion criteria #6 and #7 will be reassessed immediately prior to the plastic to study stent exchange. Patients who do not meet the inclusion criteria levels of the VAS pain score (≥ 20) and frequency of pain score (50, 75, or 100) at the time of stent exchange will be excluded from the primary effectiveness endpoint analyses but will be included in the primary safety endpoint analysis and all secondary endpoint analyses. For the patients who meet the inclusion criteria levels, we will use the scores (VAS Pain Score and Frequency of Pain Score) collected immediately prior to the plastic to study stent exchange as their baseline and include them in the primary effectiveness endpoint analyses.

Primary Safety Endpoint:

August 28, 2017

Boston Scientific
WallFlex Pancreatic Pivotal Protocol
91067616 Rev/Ver AK
Page 32 of 64

Rate of related Serious Adverse Events (SAEs) from WallFlex Pancreatic stent placement to end of study.

Relatedness will be determined by the PI, reporting if the SAE is related to the study stenting procedure, to the indwelling study stent, to study stent removal and/or to study stent migration.

Pain thought to be caused by WallFlex Pancreatic stent expansion will be reported, but will not count towards the endpoint if all three of the following conditions apply:⁵

1. Pain can be managed by medication, with the exception of injectable narcotic use for more than 24 hours.
2. Pain does not cause WallFlex Pancreatic stent removal.
3. Pain resolves by 72 hours after WallFlex Pancreatic stent placement.

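### Section 8.1.2 sets one safety hypothesis at 32% but assesses the primary safety endpoint on two different event sets, and does not say which result decides

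*Combined protocol and SAP*

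**What the plan says.** Under Related SAEs, Section 8.1.2 states one null hypothesis (rate of 32% or more), one alpha (0.025, one-sided) and one sample size (57). The aim is to show a rate "lower than 32%, the upper bound of the 95% CI of the meta-analysis". The 15% planning rate is justified by the pilot and by measures to "reduce the risk of observed related SAEs per definition of the Primary Safety Endpoint".

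The same section then says the primary safety endpoint will be assessed in two ways:

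- **Full-definition analysis:** all related SAEs, less stent-expansion pain as described in Section 4.2.
- **Pain-excluded analysis:** "one using all related SAEs except those termed as pain by the site".

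The endpoint is defined in the Synopsis, Section 4.2 and Section 8.1.1. All three contain only the narrow exclusion. Expansion pain "will not count towards the endpoint if all three of the following conditions apply": it is manageable by medication (with a limit on injectable narcotics), it does not lead to stent removal, and it resolves by 72 hours.

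On numbers, Section 8.1.2 adds 10% to 57 "for a total of 64 Intent-to-Treat patients" and allows enrolment of up to 92. Section 8.1.1 says patients below the pain thresholds at stent exchange "will be included in the primary safety endpoint analysis and all secondary endpoint analyses". Section 8.1.3 (Sensitivity Analyses) deals with missing data only.

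**The concern.** The two analyses count different events. The pain-excluded analysis would drop a related pain SAE that led to stent removal, lasted beyond 72 hours or arose from migration, provided the site called it pain. The endpoint definition counts all of these. The plan applies the name of the primary safety endpoint to both analyses. It does not call either one supportive, require both to pass or divide the alpha, and Section 8.1.3 does not make the second a sensitivity analysis.

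Followed literally, the plan yields two primary safety results against one goal, with no rule if they split. In a single-arm pivotal study whose SAEs are seen as they accrue, a rule settled after the results are known could favour the more lenient count.

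A split is plausible. Section 1.2 reports 7 SAEs in the pilot, 5 of them described as pain, and only 2 of those 5 were transient expansion pain.

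**Working it through.** **Inputs.** From Section 8.1.2: null rate 0.32, planning rate 0.15, one-sided alpha 0.025, N of 57, 64 and 92. The Synopsis specifies an exact test. Two assumptions are mine: the endpoint is the proportion of patients with at least one event, and any expansion pain excluded under Section 4.2 is also termed pain by the site. The second makes the pain-excluded events a subset of the full-definition events.

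**Step 1: reproduce the plan's figure.** The pass limit c is the largest count with P(X ≤ c) ≤ 0.025 when X ~ Bin(N, 0.32). Power is P(X ≤ c) when X ~ Bin(N, 0.15).

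| N | Limit c | Exact alpha | Power at 15% |
|---|---|---|---|
| 57 | 11 | 0.0242 | 0.862 |
| 64 | 12 | 0.0134 (13 would give 0.0273) | 0.845 |
| 92 | 20 | 0.0203 | 0.970 |

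At N=56 the power is 0.789. At 57 and every larger N checked (58 to 65, 83, 92) it stays above 0.80, so 57 reproduces. With 10% loss, 57/0.9 = 63.3, rounded up to 64. The sample size is not at fault.

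**Step 2: the full-definition analysis decides, or both must pass.** Given the subset assumption, the pain-excluded count can never exceed the full count, so whenever the full-definition analysis passes the other passes too. Requiring both is therefore the same as using the full-definition analysis alone, and the error is the alpha column above: 2.4%, 1.3% or 2.0%.

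**Step 3: the pain-excluded analysis alone may count as success.** Let s be the share of affected patients whose only counted SAEs are site-termed pain. The documents do not give s. At a true full-definition rate of 32%, the pain-excluded rate is 0.32 × (1 − s), and its pass probability is P(X ≤ c) with X ~ Bin(N, 0.32 × (1 − s)).

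| Assumed s | Pain-excluded rate | N=57 | N=64 | N=92 |
|---|---|---|---|---|
| 0 | 32.0% | 2.4% | 1.3% | 2.0% |
| 10% | 28.8% | 7.1% | 4.7% | 8.1% |
| 20% | 25.6% | 17.5% | 13.1% | 23.6% |
| 40% | 19.2% | 58.7% | 54.0% | 77.7% |

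These illustrate one reading. They are not the plan's error rate.

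**Step 4: what a split looks like.**

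- 18/57 affected misses the goal. If 7 of the 18 had only pain SAEs, 18 − 7 = 11 and the pain-excluded analysis passes.
- 20/64 misses. It takes 8, since 20 − 8 = 12.
- 29/92 misses. It takes 9, since 29 − 9 = 20.

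**Step 5: how often a split occurs at the planned 15% rate.** Under the subset assumption this is the pain-excluded pass probability at 0.15 × (1 − s) minus the full-definition pass probability at 0.15. For s from 10% to 60% it is 6.2% to 13.8% at N=57, 7.1% to 15.5% at N=64 and 2.0% to 3.0% at N=92.

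**The case against.** The strongest reply is that the documents all but answer the question. The endpoint is defined three times with the narrow exclusion only, the first analysis cites Section 4.2 by number, the 15% planning rate is tied to that definition, and the Synopsis gives a single safety test. Section 8.1.2 says the hypothesis is tested but the two analyses are merely assessed. It uses the same two-way phrasing for effectiveness, where it introduces alternative handling of missing data. On that view the pain-excluded rate is a robustness check.

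Most of this stands. The full-definition analysis is the better-supported reading, and under it no error is inflated. It is also fair that the larger figures in Step 3 rest on an assumed share and matter only under the least-supported reading. Likewise, the splits at 15% are disagreements rather than false claims, because the true rate there already meets the goal. If enrolment reaches 92, such splits are uncommon.

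The reply does not supply the missing rule. Both analyses carry the primary endpoint's name, the effectiveness wording it appeals to is unranked as well, and the deciding result still has to be inferred.

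**Conclusion.** The concern holds and should be fixed. The plan has one safety hypothesis and two unranked analyses of the primary safety endpoint, one of which omits events that the definition counts. If the Section 4.2 analysis decides, or both must pass, the one-sided error is at most 2.5% and the defect is one of wording. If the pain-excluded analysis alone could carry the claim, the 2.5% error for the defined endpoint is unprotected. How far it would be exceeded depends on the pain-only share, which the documents do not give. The pilot cannot fix that share, because it has ten patients and reports pain by event. Confidence is high that the ranking is missing; the size of the consequence is conditional.

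**What to change.** In Section 8.1.2, state that the null hypothesis of a rate of 32% or more is tested once, on the proportion of patients with at least one related SAE as defined in Section 4.2, and that this result alone decides the primary safety endpoint. State that the rate excluding site-termed pain is supportive, reported with its confidence interval and with no success claim attached.

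The cost is one or two sentences. The 57, 64 and 92 stay as they are, data collection does not change, and both rates are still reported. The sponsor gives up only the option of resting the safety claim on the pain-excluded rate. A both-must-pass rule would also control the error, but under the subset assumption it gives the same decision as the full-definition test, so naming that test is simpler.

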Primary Statistical Hypotheses	
A literature search was performed on plastic pancreatic stenting in CP. Ten (10) articles that represent 392 evaluable patients²⁻¹¹ were found.
 
Primary Effectiveness Endpoint:
 
A meta-analysis of “pain reduction” reported in these articles yielded a point estimate of 66% with a 95% Confidence Interval (CI) of 53% to 76%, using a random effects model.
 
Statistical testing will be conducted to determine if “pain reduction” using the WallFlex Pancreatic Stent is greater than 53%, assuming an observed “pain reduction” rate of 75% and using an exact test with a one-sided alpha of 0.025 and power of 80%, 43 patients will be required.
 
Primary Safety Endpoint:
 
The same literature search as above was used; however, one article, Seza et al. did not report on “related serious adverse events.” Therefore, nine (9) articles representing 386 evaluable patients were found. A meta-analysis of “related serious adverse events” reported in these articles yielded a point estimate of 25% with a 95% CI of 19% to 32%, using a random effects model.
 
Statistical testing will be conducted to determine if “related serious adverse events” is less than 32%, assuming an observed “related serious adverse event” rate of 15% and using an exact test with a one-sided alpha of 0.025 and power of 80%, 57 patients will be required.
 
Taking the larger of the two hypotheses and compensating for possible loss of patients after enrollment, an additional 10% of patients will be required, for a total of 64 patients.
 
The percentage of patients who do not meet the inclusion criteria levels of the VAS pain score (≥ 20) and frequency of pain score (50, 75, or 100) at the time of study stent placement, due to a prior single plastic pancreatic stent, is anticipated to range from 20-30%. Therefore, we propose to enroll up to 92 patients so as to have 64 patients who met the inclusion criteria levels of the VAS pain score (≥ 20) and frequency of pain score (50, 75, or 100) at the time of study stent placement.

---------------------------------------	--

August 28, 2017

Boston Scientific
 WallFlex Pancreatic Pivotal Protocol
 91067616 Rev/Ver AK
 Page 10 of 64

Table of Contents

1	Introduction	15
1.1	Literature Review.....	15
1.2	Prior Clinical Trials.....	17
1.3	Conclusion	18
2	Device Use and Description	18
2.1	Device Description.....	18
2.2	Device Use	19
3	Primary Objective	19

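### The extra 10% of patients does not offset loss when a missing 6-month score counts as failure: at 10% loss that assessment of the primary effectiveness endpoint has about 54–63% power, not 80%

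*Combined protocol and SAP*

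**What the plan says.** The effectiveness hypothesis in section 8.1.2 asks whether the probability of pain reduction "is greater than the performance goal (PG) set at 53%, the lower bound of the 95% CI from the meta-analysis above". For an assumed rate of 75%, the section asks for 43 patients, with 80% power at a one-sided alpha of 0.025. The synopsis (Primary Statistical Hypotheses) names the test: "assuming an observed “pain reduction” rate of 75% and using an exact test with a one-sided alpha of 0.025 and power of 80"%.

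The safety hypothesis needs more patients: "Assuming that the observed probability is 15%, 57 patients will be required for the above hypothesis". The larger size is then raised, "compensating for possible loss of patients after enrollment, an additional 10% of patients will be required, for a total of 64 Intent-to-Treat patients". Because patients whose pain has fallen below the entry levels at stent exchange are left out of the primary effectiveness analysis (8.1.1), 8.1.2 adds: "we propose to enroll up to 92 patients so as to have 64 patients who met the inclusion criteria levels". The ITT cohort is the primary analysis cohort (6.1.2), and withdrawn patients are not replaced (6.3).

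Missing 6-month pain data are handled in two ways in 8.1.2. One carries the last observation forward. The other is printed as "one counting patients with 6 month pain data as failures". Taken literally, this would fail every patient who has a score, so a word such as *without* must have dropped out. Section 8.1.3 supports that reading: "Missing equals failure method will be used". No power is given for this assessment.

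**The concern.** Dividing a sample size by one minus the loss rate works when lost patients are simply not analysed: enough patients remain, and the success rate among them is unchanged. When a lost patient is scored as a failure, the number analysed does not fall, but the expected success rate does. The extra patients then add to the denominator without restoring the rate on which the power was calculated.

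A reader of 8.1.2 would conclude that 10% loss has been provided for. If it has not been for one of the two assessments, a device performing exactly as assumed could miss that assessment often while passing the other. The plan does not say which of the two decides success.

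**Working it through.** **Inputs.** Null rate 53%, assumed rate 75%, one-sided alpha 0.025, exact binomial test, effectiveness size 43, safety size 57, loss 10%, total 64 (section 8.1.2; the exact test is named in the synopsis).

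**Rule.** The critical value c is the smallest count with P(X ≥ c | n, 0.53) ≤ 0.025. Power is P(X ≥ c) under the assumed rate.

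**The plan's own figures.**
- Effectiveness, n = 43: c = 30, exact alpha 0.0190, power 83.4%. With n = 42 power is 76.6%. The stated 43 reproduces.
- Safety, n = 57: reject with 11 or fewer events, exact alpha 0.0242, power 86.2%. With n = 56 power is 78.9%. The stated 57 reproduces.
- Total: 57 / 0.90 = 63.3, rounded up to 64. This reproduces.

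**Effectiveness test with 64 patients.** P(X ≥ 43 | 64, 0.53) = 0.0150 and P(X ≥ 42 | 64, 0.53) = 0.0280, so c = 43, or 43/64 = 67.2%. With complete data and a 75% rate, power is P(X ≥ 43 | 64, 0.75) = 94.0%.

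**Loss counted as failure, 75% taken as the rate among patients with a score, loss unrelated to outcome.**

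Random loss of 10%: the expected success rate is 0.75 × 0.90 = 67.5%, almost on the 67.2% needed. Power is P(X ≥ 43 | 64, 0.675) = 58.0%.

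Fixed number lost, L: power is P(X ≥ 43 | 64 − L, 0.75).

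| Lost of 64 | With a score | Power |
|---|---|---|
| 0 | 64 | 94.0% |
| 3 | 61 | 83.2% |
| 4 | 60 | 77.5% |
| 5 | 59 | 70.7% |
| 6 | 58 | 62.8% |
| 7 | 57 | 54.1% |

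Ten percent of 64 is 6.4, so both 6 and 7 belong in the range. With 7 lost, 43 of 57 patients with a score (75.4%) must succeed, slightly more than the 75% assumed. With random loss, 80% power is kept up to about 5%: 80.6% at 5.0% loss and 79.8% at 5.2%.

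For contrast, if the 7 lost patients left the denominator, n = 57 would need 39 successes and have 90.1% power. That is the setting in which the increase does its job, but dropping patients is not a planned effectiveness analysis.

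**Loss counted as failure, 75% taken as the rate in all patients.** Let s be the share of the lost 10% who would have responded. The observed success rate is 0.75 − 0.10 × s, and power is P(X ≥ 43 | 64, that rate).

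| s | Success rate | Power |
|---|---|---|
| 0 | 75.0% | 94.0% |
| 0.25 | 72.5% | 86.2% |
| 0.50 | 70.0% | 73.8% |
| 0.75 | 67.5% | 58.0% |

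**More than 64 in the effectiveness analysis.** If only 20% of 92 miss the pain levels, 0.80 × 92 = 73.6, so 73 or 74 are analysed. At 10% random loss (rate 67.5%) power is 67.5% with 73 and 64.5% with 74.

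**The case against.** *The plan makes no arithmetic error.* This stands. 43, 57 and 64 are all right, the 80% is attached to 43 patients, and the 10% was added to the safety size. Effectiveness gets 64 − 43 = 21 patients more than it needs with complete data. But the power figures above already use all 64, and that surplus does not absorb 10% loss scored as failure.

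*The low figure depends on what 75% means.* This also stands. Section 8.1.2 defines the parameter only as the probability of observing pain reduction, and ties 75% to 8 of 10 pilot patients, counted over everyone. If 75% is an all-patient rate and those lost are mostly non-responders, power remains at or above 80%. Allowing for loss separately suggests that 75% is meant for patients with data, but the documents do not say so. The result must therefore be given as a range.

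*Counting missing as failure is only a sensitivity analysis.* Section 8.1.3 does place it under that title, as the tipping-point mechanism. But 8.1.2 lists it as one of two ways in which the primary endpoint will be assessed and mentions the tipping-point analysis separately. It is also true that low power in a conservative assessment does not raise the type I error.

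*Stronger readings.* A reader might infer that the effectiveness objective as a whole is underpowered. The documents do not support that: the shortfall belongs to one of two assessments, and which one decides is not stated. Nor do they support a definite power for the carried-forward assessment, since that depends on how often carried-forward scores meet the definition of relief. A reader might also infer that ITT patients who never receive a stent count as failures and lower the power further. No section says so, and the 64 are defined by pain levels at study stent placement.

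**Conclusion.** The concern holds for the missing-equals-failure assessment. The 10% increase does not compensate for loss there, and the 80% power does not carry over to it at the loss rate the plan allows for. With 64 patients and 10% loss, power is about 54–63%. This rests on three assumptions: 75% applies to patients with a 6-month score, loss is unrelated to outcome, and the misprint is read as *without*. On those assumptions a device performing as assumed would miss this assessment about 37–46% of the time. If 75% is the rate in all patients, the figure is about 74% when half of those lost would have responded and 94% when none would.

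This is a statement about power that the plan makes too broadly. It does not show that the sample size was miscalculated or that the trial needs to be larger.

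**What to change.** 1. In 8.1.2, correct the description of the second assessment so that patients *without* 6-month pain data count as failures.
2. In 8.1.2 and the synopsis, state the power of that assessment with 64 patients beside the 94% for complete data: about 54–63% at 10% loss if 75% applies to patients with a score and loss is unrelated to outcome; about 74% to 94% if 75% is the all-patient rate and between half and none of those lost would have responded. Add that, under the first assumption, 80% is kept only up to about 5% random loss, or 3 of 64 lost.
3. Limit the statement that the extra 10% compensates for loss to analyses in which lost patients leave the denominator.

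The cost is wording in two places. No patients are added, and the test and the performance goal stay as they are. The plan will show a less favourable power for one of its two assessments.
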